10.2 Selection

We test this explanation by testing its assumptions or predictions:

- Individuals who were differentially sick or risk averse at baseline are more likely to enroll in RSBY in the first place and/or retain the RSBY card at midline and endline, conditional on household group assignment.
- Total utilization should be weakly higher in household group A than C. Equivalently, average utilization including both enrollees and non-enrollees, i.e., the ITT estimates of utilization, should be higher in A.¹⁹
- After predicting those in group A likely to enroll if they were in group C, we test to see if they have higher utilization conditional on getting insurance.

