5.2 Treatment assignment

We designed a two-stage randomization process to study both direct treatment and spillover effects of health insurance.

In a first stage, we randomly assigned villages to one of five village-level arms. A village-level arm is defined by the percentage of households within the village assigned to each of the four household-level study arms defined in subsection 4.2.1. The percentage allocations to the 4 household-level arms are given in the last 4 columns of Table 1. The percent of villages assigned to each of the 5 village-level arms are in the second column. Villages were matched before this first stage randomization.⁷

Table 1: IHIE Two-Stage Randomization Design

Village-level arms (%)		Household-level arms (%)			
Arm	Village allocation	Group A	Group B	Group C	Group D
I	15	30	50	10	10
II	15	30	10	50	10
III	15	30	10	10	50
IV	35	70	10	10	10
V	20	10	30	30	30
Total	100	40	20	20	20

In a second stage, we randomly assigned households within a village to the four arms according to the allocation probabilities assigned to the village. Households were matched before this second stage randomization.⁸

The target enrollment for each of the 4 household-level arms, unconditional on village-level arm, was 4,500 households for condition A and 2,250 households for each of conditions B, C and D. Due to some attrition between listing and completion of baseline, our final randomized sample amounted to 11,089 households in 424 villages in the two districts.

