5.4 Treatment Delivery

The population that is eligible for this study would not be eligible for RSBY under the program's usual rules. To make this study possible, we exchanged letters of cooperation with the state in which we conducted the study (Karnataka), the central government agency (Ministry of Labor) responsible for administration of RSBY, and the development organization (GIZ) providing technical support for RSBY.

Sample households were randomized in August 2014 using data from the listing exercise. They were informed of their treatment assignment and, depending on which arm to which they are assigned, given access to insurance or cash in May and June 2015. This step took place roughly 18 months after the baseline due to government constraints. Due to challenges associated with evaluating a government program, we were only able to enroll sample households when the government held its RSBY enrollment drive in early 2015.

We enrolled study households much in the same way the government enrolled RSBY (non-study) eligible households into the program: via a mobile enrollment truck that visited each village. One difference is that we went to each household to ask them if they would like to enroll and took them to the enrollment truck, which was parked in one place in the village. By contrast, the government informed non-study households by delivering paper notices (chits) to each home about when and where the enrollment truck would be in the village.

Roughly 78.4%, 70.4% and 58.6% of households in arms A, B, and C, respectively enrolled in RSBY. Enrollment rates are somewhat higher in Gulbarga than Mysore: 77.9/76.4/64.1% v. 78.8/63.5/52.3% in A/B/C. No one in arm D enrolled.

For all study households that take up insurance, we paid the government their premiums. For households in arms A, this was funded by grant funds. For those in B and C that purchase insurance, this was funded by the respondents' money.

The Karnataka government renewed RSBY automatically for non-study and study households in 2016 and 2017 without any action—even payment—by enrollees. RSBY ended in the state on August 31, 2018, to make way for the new NHPS scheme, which is scheduled to start in late 2018 or early 2019. As of this writing, Karnataka had agreed to roll out NHPS but had not begun the roll-out.

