11. Age or child/adult status
12. Marital status, birth order and relationship to household head
13. Size of village
14. Percent of village assigned to access to RSBY via this RCT
15. Percent of village eligible for RSBY outside the RCT
16. Hospital utilization in prior year (measured at baseline) or predicted hospitalization
17. Health status or serious sickness
18. Cognitive capacity
19. Willingness to pay for insurance (predicted based on data from a randomly selected sample of households removed from main RCT and chosen to participate in a WTP study)
20. Risk and time preferences
21. Assets and savings
22. Urban, peri-urban, and rural status
23. Monthly expenditure budget
24. Experiencing a serious health shock in the past year (provided this is balanced across treatment arms)

Predicting utilization. A natural dimension along which the impact of insurance may differ is the latent propensity of a household to experience health shocks which would require inpatient care. Since this variable is latent, it must be estimated. We will machine learning methods to predict households' likelihood to experience an inpatient hospitalization. We will perform this exercise on two samples: the baseline data (across all treatment arms) and the post-intervention data (using only group D, the control group). The resulting model will then be used to generate predictions for the full sample. Our key hypotheses are (1) that the impact of the offer of insurance will lead to larger treatment effects for those with higher propensity; and (2) that demand for insurance will be less price-elastic among those with higher propensity (i.e., adverse selection). Hypothesis (2) will be tested by examining how takeup of insurance varies between free and not free (group A vs. groups B and C) for high- vs. low-propensity households.

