8.5 General coloring variables

The following is a non-exhaustive list of variables that may be used as control variables that measure dosage, specific margins of response or dosage. This list is non-exhaustive as it lists only those variables measured at endline and not otherwise included as a coloring variable above.

- Gender of respondent
- Age of respondent
- Role of respondent in household (relationship to head of household)
- Size of household
- Number of adults in household
- Number of children in household
- Knowledge of BPL households and how many
- Knowledge of BPL households with RSBY cards and how many
- Knowledge of household that successfully used RSBY
- Knowledge about RSBY (number correct out of 4 questions)
- Knowledge of when RSBY scheme expired
- Subjective willingness-to-pay for RSBY
- Knowledge about NHPS
- Does respondent think household is covered by NHPS
- One item test of NHPS (does respondent know about amount of coverage)
- Did any other individuals assist with answering questions during the survey? If so, what is the gender and relationship to respondent? ¹⁷

¹⁷Additional respondents may affect the response quality in both positive and negative ways. For finance questions, these individuals may improve the precision of the responses. For health questions, these individuals may lead to decreased precision. Please note that enumerators were instructed to administer health questions without any additional individuals present to minimize this concern.

9 Structural modeling

We plan to develop an economic model of household financial decisions and health status. We will structurally estimate the model using the experimental variation, to quantitatively reconcile the rich set of empirical results and perform counterfactual analysis.

10 Why is higher price for insurance associated with higher utilization?

At midline we found that individuals in group C, which had to pay a premium for insurance but did not get an unconditional cash transfer, had higher rates of utilization of the RSBY card. We will explore three explanations. First, individuals that value insurance more because they are more likely to use it are more likely to take up insurance, i.e., there is selection. Second, a higher price for a good sends a positive signal about the quality of the good, and higher quality goods are consumed more. Third, there is some sunk cost effect.

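### The enrolment test for selection in Section 10.2 works within arms, so it can be positive when paying draws no sicker a pool than free enrolment; the other two tests do not close the gap

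*Combined protocol and SAP*

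**What the plan says.** The introduction to Section 10 reports that at midline group C, which paid and received no cash, "had higher rates of utilization of the RSBY card". It does not give the size of the difference or say whether the rate is per enrollee or per assigned household. Selection, price signaling and sunk cost are the three candidate explanations.

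Section 10.2 gives three tests of selection:

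1. "Individuals who were differentially sick or risk averse at baseline are more likely to enroll in RSBY in the first place", or keep the card to midline and endline, conditional on household arm.
2. Intent-to-treat utilization should be at least as high in A as in C.
3. "After predicting those in group A likely to enroll if they were in group C, we test to see if they have higher utilization", given that they are insured.

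No rule says how the three combine. Section 10.4 names no test of sunk cost and treats failure to support the other two explanations as evidence for it.

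Section 7.3 has a contrast between free and paid arms: the check on adverse selection consists of "examining how takeup of insurance varies between free and not free (group A vs. groups B and C) for high- vs. low-propensity households". It concerns predicted inpatient propensity, and Section 10.2 does not refer to it.

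On uptake, Section 5.4 states: "Roughly 78.4%, 70.4% and 58.6% of households in arms A, B, and C, respectively enrolled in RSBY".

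**The concern.** The quantity to be explained is a difference between arms. Selection produces such a difference among enrollees only if charging a price changes who enrols, so that C's pool is more prone to use care than A's. The first test asks something else: whether sick or risk-averse households enrol more at a given price. If they are over-represented to the same degree whether RSBY is free or paid for, the test is positive and the two pools are alike.

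How prices affect utilization is evaluation question 2 in Section 3. Because sunk cost is only a residual in Section 10.4, mistaken support for selection also removes the only evidence that the plan would count for sunk cost.

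**Working it through.** The plan gives no figure for the part of the C-A difference due to selection, so there is nothing to reproduce.

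**Inputs from the documents.** Enrolment of 78.4% in A, 70.4% in B and 58.6% in C (Section 5.4). The district rates agree: the B and C rates imply a Gulbarga weight of about 0.53, and 0.53 × 77.9 + 0.47 × 78.8 = 78.3% for A. Section 5.2 gives 11,089 households; at 40/20/20% this is about 4,436 in A and 2,218 each in B and C.

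**Assumed.** 30% of households sick at baseline; sick enrollees use the card 3 times as often as well enrollees.

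**Step 1: when do the pools differ?** Sick share of enrollees = 0.3 × P(enrol | sick) / P(enrol). With r the sick-to-well enrolment ratio, this is 0.3r / (0.7 + 0.3r). It depends on the arm only through r.

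**Step 2: no differential selection (r = 1.15 in every arm).**
- A: well 0.784/1.045 = 75.0%, sick 86.3%, gap 11.3 points.
- C: well 0.586/1.045 = 56.1%, sick 64.5%, gap 8.4 points.
- Sick share of enrollees: 0.345/1.045 = 33.0% in both arms. Selection explains 0%.

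**Step 3: the three tests in that setting.**
- *Test 1.* The gaps are 11.3, 10.1 and 8.4 points in A, B and C, with SEs of 1.22, 2.01 and 2.24 from s(1−s)/(0.3n) + w(1−w)/(0.7n), where s and w are the sick and well enrolment rates. Inverse-variance pooling gives 10.5 points, SE 0.95, z about 11. Positive.
- *Test 2.* Let paying raise use per enrollee by a factor k for reasons other than selection. Use per assigned household is 0.784u in A and 0.586ku in C. A stays at or above C unless k exceeds 0.784/0.586 = 1.34. At k = 1.25 it is 0.784u against 0.733u. Positive.
- *Test 3.* Weight A enrollees by the predicted chance of enrolling under C (64.5% sick, 56.1% well). Sick share of likely C enrollees: 0.330 × 0.645 / (0.330 × 0.645 + 0.670 × 0.561) = 36.2%. Of the rest: 0.330 × 0.355 / (0.330 × 0.355 + 0.670 × 0.439) = 28.5%. Use ratio: (1 + 2 × 0.362)/(1 + 2 × 0.285) = 1.10. Positive.

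All three favour selection, although the pools are identical and the whole difference comes from k.

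**Step 4: the scale matters.** In Step 2 the additive gap is smaller in C (8.4 against 11.3 points) although composition is the same. Conversely, a constant 10-point gap gives sick shares of 32.7% in A (0.3 × 0.854/0.784) and 33.6% in C (0.3 × 0.656/0.586), and a C/A use ratio of 1.011 (1.007 to 1.016 for 2-fold to 5-fold use). The contrast that tracks composition is on the ratio scale.

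**Step 5: what real differential selection looks like.** With gaps of 0 points in A and 20 in C, the sick shares are 30.0% and 37.2%, and the use ratio is (1 + 2 × 0.372)/(1 + 2 × 0.300) = 1.09.

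**Step 6: precision of the arm contrast.** With no sickness effect, the additive C v A interaction has variance 0.784 × 0.216/(4,436 × 0.21) + 0.586 × 0.414/(2,218 × 0.21), so SE 2.65 points; with the 10-point gap it is 2.55. Taking about 2.6, an assumed design effect of 2 for villages gives 2.6 × 1.41 = 3.7 points. Before clustering, the smallest interaction detectable with 80% power is 2.80 × 2.65 = 7.4 points.

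**The case against.** The strongest reply is that test 1 is one of three and reads naturally as an assumption check: if sickness does not predict enrolment, selection on sickness fails. That stands, and it is why the test should be kept as a necessary condition. Test 2 can also refute pure selection: if C exceeds A per assigned household, the per-enrollee ratio is above 1.34. If the midline finding is itself per assigned household, test 2 would already count against selection. But passing test 2 is weak support, since higher uptake in A alone produces it.

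Test 3 does aim at those who would enrol at a price. If the prediction were of enrolling under C among those who enrol when it is free, the Step 2 contrast would vanish: 64.5/86.3 and 56.1/75.0 are both 0.747. The plan specifies neither that prediction nor any comparison with C.

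Three stronger readings are tempting but unsupported:

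- *That selection explains about 1% of the C-A difference.* The 1.011 in Step 4 is a use ratio under assumed inputs. A share needs the size of the gap: 1.1% is 22% of a 5% gap, 4.4% of a 25% gap and 1.1% of a 100% gap. Other assumptions (a constant odds ratio up to 5, gaps of 25 to 100%) take the share from 0% to about 44%.
- *That the plan has no free-versus-paid contrast.* Section 7.3 has one, though not for sickness or risk aversion and not linked to Section 10.2.
- *That selection would be declared on test 1 alone.* No such rule is written; the gap is that no rule is given at all.

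**Conclusion.** The concern holds in a limited form. The first test in Section 10.2 cannot by itself separate selection that is the same at every price from selection induced by price. The other two tests can agree with it when the pools are identical, as long as the price effect on use per enrollee is below about 1.34. Selection could then be called supported while explaining little or none of the C-A difference.

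The 1.34 rests only on the plan's uptake figures. The z of about 11 and the sick shares rest on the assumed 30% sick and the assumed enrolment ratio; the result for test 3 also rests on 3-fold use and on predicting from C enrolment alone. None allows for village clustering. The point affects a mechanism analysis, not the main treatment effects.

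**What to change.** In Section 10.2:

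1. Test whether baseline sickness and risk aversion differ between enrollees in C (and in B) and enrollees in A. Equivalently, fit an arm-by-characteristic interaction in 2015 enrolment on the ratio scale, with village-clustered errors. Present this as an extension of the free v not-free contrast in Section 7.3.
2. Re-weight A enrollees to the baseline profile of C enrollees and report, with a confidence interval, how much of the C-A gap in use per enrollee closes.
3. Keep the within-arm association as a necessary-condition check that does not count alone as support, and state how the tests combine.
4. Amend Section 10.4 so that a null result on the arm contrast is not read as evidence for sunk cost.

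The cost is SAP wording, one interaction model and one re-weighted comparison, using baseline and 2015 enrolment data already collected and the card-use data from midline and endline. The downside is precision: the C v A contrast has an SE of about 2.6 points on the additive scale before clustering, against about 0.95 for the within-arm association. Modest differential selection may go undetected, which is why item 4 is needed. Re-weighting also adjusts only for characteristics measured at baseline.

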5.3.6 Endline Survey

In March - May 2019, we will be conducting a 4 year follow-up survey. We will survey 1 member (our first priority is to interview the female most knowledgeable from baseline (or midline for households with missing baseline data), followed by the current female most knowledgeable, and then the male most knowledgeable) of each household in the sample. Respondents will be asked about subjective health status, health care consumption and financial status. Households will be paid a participation incentive comprised of bars of soap and tubes of toothpaste valued at approximately INR 50 for completing major sections of the survey. We will perform backchecks on 10% of households, a rate known to surveyors *ex ante*.

Rounds (1) – (3) were conducted on paper and the remainder on tablets. Rounds (1) – (4) were conducted by IFMR and the midline (5) by Nielsen. The endline will be conducted by Outline India.

⁹The actual rate is 4 households per village on each module of the the survey.

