8.1 Demand for insurance

8.1.1 Uptake

- Take up RSBY at enrollment (in 2015)

¹⁴We will also consider multiple testing approaches as raised in Lee and Shaikh (2014).

- Possession of RSBY card at endline
- Possession of RSBY card in past
- No longer have RSBY card
- Number of household members on RSBY card

Coloring variables

- Date RSBY card acquired
- Why household no longer has RSBY card
- Expected RSBY card but did not receive it

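### Card retention should not count as evidence of selection or demand in 10.2 and 8.1.1: renewal was automatic and free, RSBY had ended before endline, and retention at midline can be a consequence of use

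*Combined protocol and SAP*

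**What the plan says.** Section 10 offers three explanations for the midline finding that arm C used the card more: selection, price signaling and sunk costs. It describes selection as people who expect to use insurance more being more likely to take it up. The first prediction tested in Section 10.2 is that households differing in baseline sickness or risk aversion are, given their arm, "more likely to enroll in RSBY in the first place and/or retain the RSBY card at midline and endline". Two further predictions follow: total utilization in A against C, and utilization among the arm A households predicted to enroll had they been in C.

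Section 8.1.1, under the demand heading, lists 2015 take-up first. It then includes "Possession of RSBY card at endline" and "No longer have RSBY card", along with past possession and the number of members on the card.

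On how cover continued, Section 5.4 says "The Karnataka government renewed RSBY automatically for non-study and study households in 2016 and 2017" and that this happened "without any action—even payment—by enrollees". It also says "RSBY ended in the state on August 31, 2018". On timing, Section 5.3.6 says "In March - May 2019, we will be conducting a 4 year follow-up survey".

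**The concern.** Selection into insurance concerns who chooses cover. For the study offer, the plan describes one such choice: enrollment in May and June 2015. It describes no later point at which an enrolled household renewed, paid for or dropped that cover. Whether the card is still in the house is settled after enrollment and can depend on whether it was used.

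The wording in 10.2 joins enrollment and retention with an and/or, so a difference in retention alone can be read as support for selection. This also affects the third explanation. Section 10.4 pre-specifies no sunk-cost test and treats failure to support the other two explanations as evidence for sunk costs. False support for selection would therefore weaken the sunk-cost reading as well.

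In 8.1.1 the stake is what the demand family measures. Section 7.4 says an index is built from all the outcomes in each Section 8 group. Section 8 says index items will be indicated, but 8.1.1 marks none. Unless this is settled, custody of an expired card could enter a demand index.

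**Working it through.** The plan gives no sample size, power or error rate for this test, so there is no figure of its own to reproduce. The check has two parts.

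**1. Dates.** RSBY ended on 31 August 2018 (5.4). Endline runs from March to May 2019 (5.3.6).
- To 1 March 2019: 182 days / 30.44 = 6.0 months after the end.
- To 31 May 2019: 273 days / 30.44 = 9.0 months after the end.

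Midline ran from November 2016 to February 2017 (5.3.5), which is 21.9 to 18.0 months before the end. Cover was live at midline and had lapsed at endline.

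**2. Can retention differ by sickness with no selection at enrollment?** Let u be the share of enrollees who use the card, k1 the share of users who keep it and k0 the share of non-users who keep it.

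Retention = u × k1 + (1 − u) × k0

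Gap, sick minus healthy = (u_sick − u_healthy) × (k1 − k0)

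The gap is zero only if use does not differ by sickness or keeping does not depend on use.

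Inputs from the plan:
- Enrollment of 78.4%, 70.4% and 58.6% in A, B and C (5.4).
- Targets of 4,500, 2,250 and 2,250 for those arms, and 11,089 households randomized (5.2). The four targets sum to 11,250.
- Enrollees at target: 4,500 × 0.784 + 2,250 × 0.704 + 2,250 × 0.586 = 6,430.5.
- Scaled to the randomized sample: 6,430.5 × 11,089 / 11,250 = about 6,338.

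Assumptions not in the plan:
- 25% of households are sick at baseline, and they use the card twice as often as the others.
- 60% of non-users keep the card.
- Tests are two-sided at 5%, stratified by arm, with retention tested among enrollees.
- There is no attrition and no village clustering.

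Enrollment was set independent of sickness. Rejection rates over 4,000 simulated trials:

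| Use, sick v healthy | Keep, user v non-user | Retention, sick v healthy | Enrollment test | Retention test | Either test |
|---|---|---|---|---|---|
| 20% v 10% | 60% v 60% | 60.0% v 60.0% | 5.1% | 4.6% | 9.6% |
| 10% v 5% | 90% v 60% | 63.0% v 61.5% | 4.8% | 18.6% | 22.4% |
| 20% v 10% | 80% v 60% | 64.0% v 62.0% | 5.0% | 29.3% | 32.9% |
| 20% v 10% | 90% v 60% | 66.0% v 63.0% | 5.1% | 56.7% | 59.1% |
| 30% v 15% | 90% v 60% | 69.0% v 64.5% | 5.5% | 91.7% | 92.2% |

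Hand check of the fourth row:
- Pooled retention is 0.25 × 0.66 + 0.75 × 0.63 = 0.6375.
- SE = sqrt(0.6375 × 0.3625 × (1/1,585 + 1/4,753)) = 0.0139.
- 0.03 / 0.0139 = 2.15, and the normal probability of 2.15 − 1.96 = 0.19 is about 0.58, in line with 56.7%.

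The share counted as sick matters. With half sick, SE = sqrt(0.645 × 0.355 × 2/3,169) = 0.0120, the ratio is 2.50 and rejection is about 70%.

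The enrollment test stays at its nominal level throughout. Counting either limb as support costs something even when keeping is unrelated to use: 1 − 0.95² = 9.75%, against 9.6% simulated.

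**The case against.** The case on the other side has real force, and it limits several stronger readings that a reader might infer.

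- **That retention carries no information at any round.** The documents do not support this for midline. The smart card is the means of delivering the benefit (4.2), and cover was still running. Keeping the card then preserved usable insurance, so midline retention may partly reflect how much it was valued. Free renewal removes a renewal decision; it does not remove the value of holding the card.
- **That no household could acquire RSBY after mid-2015.** The plan records when the card was acquired and whether the household now has a BPL card, and BPL status confers eligibility (4.2). Later acquisition outside the study offer is possible.
- **That past possession is equally compromised.** It measures whether a household ever had a card, and keeping the card because it was used does not bias that.
- **That the selection verdict rests on retention.** Section 10.2 states no rule that one limb of one prediction suffices, and its other two predictions do not use retention. The and/or is a loose wording that permits a bad reading; it does not require one.
- **That use is the main reason cards are kept.** The plan does not say so, and the use and keeping rates above are assumed. If users kept the card less often, the gap would reverse. Standard errors clustered by village, as 7.1 specifies, would also change the rejection rates.

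The plan also collects the reason a card is no longer held, when it stopped being valid, and whether the respondent knows when the scheme expired. These could help separate loss, expiry and disuse, but they are listed only as coloring variables and 10.2 does not build them into the test.

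None of this rescues endline possession as evidence of selection or demand, or makes midline retention a decision to take up cover.

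**Conclusion.** The point holds in a limited form. Endline card possession, 6 to 9 months after RSBY ended and following free automatic renewals, reflects no insurance choice and should not count as evidence of selection or demand. Midline retention is ambiguous: it may carry some information about value, but it comes after use and cannot establish selection alone.

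The direction and size of any distortion in this trial are unknown. The 5% to 92% range depends on assumed use, keeping and sickness rates, covers the sickness limb only, and ignores clustering and attrition. It shows that a retention test can reject often when there is no selection at enrollment. The two other predictions in 10.2 and the 2015 take-up outcome in 8.1.1 are unaffected. The change is worth making because it closes an avoidable route to false support, which would carry through to the by-elimination sunk-cost inference in 10.4.

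**What to change.** In Section 10.2, rewrite the first prediction along these lines: *Within each of arms A, B and C, we test whether baseline sickness and risk aversion predict enrollment in 2015. Card retention at midline is reported separately as a secondary result and cannot by itself establish selection. Card retention at endline is not used as evidence of selection.* Leave the other two predictions as they are.

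In Section 8.1.1, name 2015 take-up as the demand outcome. Report endline possession and loss of the card descriptively, outside any demand index, alongside the recorded reasons for loss. Past possession may stay as an ever-covered measure.

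The amended plan is dated 24 June 2019, after the planned endline window. Date the change and state whether the retention data had been examined.

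The cost is small. No new data are needed and every item is still reported. The downside is that one supplementary retention signal no longer counts as evidence of selection or demand.
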